9 STUDY DESIGN/STUDY ENDPOINTS

This will be a prospective, randomized, double-blinded, single center study of the impact of a short course of furosemide on postpartum blood pressure recovery in women with hypertensive disorders of pregnancy (HDP). Please refer to Section 2.4 for end points.

Regarding stopping rules for safety or efficacy, we do not anticipate early termination of the study for either. Issues that would be of concern would be persistent hypokalemia (< 3.0) with therapy, ineffectiveness of therapy (as defined by the use of the same dosing of other antihypertensive agents for blood pressure control), and unexpected events (admission to ICU). Other findings that could trigger a safety review include the number of SAEs overall, the number of occurrences of a particular type of SAE, severe AEs, or increased frequency of events.

9.1 Sample Size and Accrual

The sample size is based on a current ongoing study at HUP in which 45.6% of patients had persistently elevated blood pressures 7 days after delivery. For a power of 80% and a statistical significance level of 5%, 175 patients would be needed to find a 40% reduction in blood pressures with the use of furosemide. In anticipation of possible post-randomization losses of approximately 10% of patients, we plan to recruit 385 participants for randomization in the two groups.

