2 STUDY AIMS

- **2.1 AIM 1:** To compare the rate of persistently elevated blood pressures 7 days postpartum in women that receive a five day furosemide course compared to those that receive placebo
- **2.2 AIM 2:** To compare the time (days) required to achieve a resolution of elevated blood pressure.

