2.3 Endpoints

2.3.1 Primary endpoint

- **2.3.1.1** Postpartum hypertension composite outcome, defined as:
 - Persistently elevated blood pressure (≥140/90) at 7 days postpartum OR
 - Additional requirement of antihypertensive agents after randomization

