9.2 Data Analyses Plans

To account for the multiple measurements per patient, we will employ repeated measure regression techniques. Measures of relative risk will include 95% confidence intervals. Descriptive statistics will be presented as mean with standard deviation, median with interquartile range, or proportion with 95% confidence interval based on data type and distribution. Comparisons between groups will be performed using a Chi-square or Fisher's exact test for categorical variables and parametric or non-parametric tests for continuous variables, as appropriate. Bivariable analysis will be used to determine variables (risk factors) that are independently associated with PPHTN. Intention-to-treat analyses will be conducted such that all patients with available follow-up measures will be included in the analysis. Blood-pressure measurements after randomization will be compared between groups with the use of a mixed-effects logistic-regression model, which will account for participants having different numbers of observations over a varying time span. Statistical analyses were conducted in SAS, version 9.4 (SAS Institute, Cary, NC). Two-tailed P values of <0.05 will be considered statistically significant.

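### Section 9.1's sample size, effect and power disagree: 175 per arm gives about 95% power, not 80%, for a 40% relative reduction from 45.6%, and the rate used is not for the composite primary endpoint

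*Combined protocol and SAP*

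**What the plan says.** Section 9.1 bases the sample size on an ongoing study at the same hospital in which "45.6% of patients had persistently elevated blood pressures 7 days after delivery". At 80% power and 5% significance it concludes that "175 patients would be needed to find a 40% reduction in blood pressures with the use of furosemide". It then allows for about 10% losses and ends with "we plan to recruit 385 participants for randomization in the two groups".

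Section 9.2 adds that "Two-tailed P values of <0.05 will be considered statistically significant" and that "Measures of relative risk will include 95% confidence intervals". It names the chi-square or Fisher's exact test for categorical comparisons. Section 1.2 assigns half of the women to placebo.

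On the outcome, Aim 1 in section 2 is "To compare the rate of persistently elevated blood pressures 7 days postpartum". The primary endpoint in 2.3.1 is a composite: blood pressure of at least 140/90 at day 7, or "Additional requirement of antihypertensive agents after randomization".

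**The concern.** There are two problems in the same paragraph.

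First, the control rate, effect, power, significance level and sample size in 9.1 are not free of one another. Any four fix the fifth, and the five printed do not fit together. A reader cannot tell whether the trial was designed to detect a 40% reduction with high power or a smaller reduction with 80% power. That matters most if the result is null, because the conclusion then depends on which effect the trial could have detected.

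Second, the calculation concerns a different outcome from the one to be tested. The 45.6% describes the Aim 1 outcome, which is only the first component of the primary endpoint. The second component cannot be assumed negligible, since sections 4.3 and 5.3 provide for antihypertensive treatment in either arm when raised pressures persist after delivery.

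**Working it through.** **Inputs.** Control rate p1 = 0.456 (9.1). A 40% reduction read as relative: p2 = 0.456 x 0.60 = 0.2736, a difference d = 0.1824. Two-sided alpha 0.05 (9.2), so z = 1.960. Power 80% (9.1), so z = 0.8416. Allocation 1:1 (1.2).

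**Accrual.** 175 x 2 = 350, and 350 x 1.10 = 385. This reproduces the plan's total, so 175 is per arm. Read as a total, 175 x 1.10 = 192.5, which is not 385. (Dividing by 0.90 instead would give 389, a trivial difference.)

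**Sample size per arm.** n = [1.960 x sqrt(2 x pbar x (1 - pbar)) + 0.8416 x sqrt(p1(1 - p1) + p2(1 - p2))]^2 / d^2, with pbar = 0.3648.

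- First term: 1.960 x sqrt(2 x 0.3648 x 0.6352) = 1.3343
- Second term: 0.8416 x sqrt(0.456 x 0.544 + 0.2736 x 0.7264) = 0.5626
- n = (1.8968)^2 / 0.03327 = 108.1, so **109 per arm**
- Continuity-corrected, (n/4) x [1 + sqrt(1 + 4/(n x d))]^2 = 118.9, so **119 per arm**

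That is 218 to 238 evaluable women, against 350 planned.

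**Power at 175 per arm.** z = (0.1824 x sqrt(175) - 1.3343) / 0.6684 = (2.4129 - 1.3343) / 0.6684 = 1.614, so power is **94.7%**. With continuity correction it is 93.3%, and by Fisher's exact test 93.5%. After 10% losses, 385 x 0.90 = 346.5, or 173 per arm: 94.4% (93.0% corrected). With 175 as the total (87.5 per arm), power would be 71%.

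**Effect detectable with 175 per arm at 80% power.** Solving for p2 gives 0.311, a 31.8% relative reduction or 14.5 points. With continuity correction it is 0.305, 33.0% or 15.1 points.

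**Other readings of the 40%** (two-sided 5%, 80% power):

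| Scale of the 40% | p2 | n per arm | n corrected |
|---|---|---|---|
| Relative risk 0.6 | 0.274 | 109 | 119 |
| Hazard scale, 1 - 0.544^0.6 | 0.306 | 164 | 177 |
| Odds ratio 0.6 | 0.335 | 254 | 270 |
| 40 absolute points | 0.056 | 18 | 23 |

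Keeping the relative reading and changing another input does not give 175 either: one-sided 86 (96 corrected); 90% power 145 (156); 95% power 179 (189). Two unstated routes come close. One is the corrected hazard-scale figure of 177. The other is a 40% relative reduction diluted by 20% non-adherence, p2 = 0.456 x (1 - 0.40 x 0.80) = 0.3101, which needs 174 (187 corrected). The documents mention neither for this calculation.

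**The composite.** In the same population its control rate cannot be below 45.6%, because it adds a second way to have an event. Beyond that, its power depends on the rescue rate, the effect on rescue and the overlap of the components, none of which is given. The examples below use assumed rescue rates, 175 per arm and a 40% relative reduction in the day-7 component:

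- Rescue 20% in both arms, independent of day-7 status: 1 - 0.544 x 0.80 = 0.565 against 1 - 0.7264 x 0.80 = 0.419; power 78%.
- Rescue 20%, every rescued woman also raised at day 7: 0.456 against 0.274; power 94.7%.
- Rescue 40% in both arms, independent: 1 - 0.544 x 0.60 = 0.674 against 1 - 0.7264 x 0.60 = 0.564; power 56%.
- Rescue 20% on placebo and 12% on furosemide, independent: 0.565 against 1 - 0.7264 x 0.88 = 0.361; power 97%.

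These are illustrations, not a range. They show that power for the primary endpoint cannot be read from the plan.

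**The case against.** The strongest reply is that the discrepancy is conservative: on the relative reading the trial is larger than it needs to be, so nobody is harmed by an underpowered comparison. That stands for day-7 blood pressure on the relative scale, but not beyond it. If an odds ratio of 0.6 was meant, 175 per arm has about 64% power.

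The scale itself can also be disputed. The planned relative risks favour a relative reduction, yet section 9.2 also plans a mixed-effects logistic model for blood pressures after randomization, which works on the odds scale. The objection is fair: 9.2 leans towards the relative reading but does not settle it. It does not rescue the 175, because none of the readings that the documents support gives that number.

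On the endpoint, Aim 1 can be seen as narrower than the composite and not in conflict with it, and the 45.6% may have been meant as a proxy. The source study is not available, so it is unknown how women already treated were counted in it. The plan nevertheless gives no reason for using the day-7 rate in place of a composite rate.

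**Conclusion.** The point holds. For a 40% relative reduction from 45.6%, two-sided 5%, the stated 80% power needs 109 to 119 per arm. The planned 175 gives about 95% (93.3% with continuity correction), and 94.4% (93.0%) after the planned losses. The gap is about 15 points of power, or 66 women per arm (175 - 109), too large for rounding or choice of formula to explain. This rests on reading the 40% as relative, which 9.1 does not say. What does not depend on the scale is that the printed inputs yield no 175, and that the primary composite has no stated control rate, effect or power. No shortfall is shown for day-7 blood pressure on the relative reading. For the composite, adequacy cannot be judged either way. This should be fixed, but it does not by itself put the design in doubt.

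**What to change.** In section 9.1:

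- State that 175 is per arm, name the test (and whether it is continuity-corrected), and give the scale of the 40% as a reduction in the proportion with raised pressure.
- Restate one figure: either power of about 95% for a 40% relative reduction, or about a 32-33% relative reduction (14.5-15.1 points) at 80% power. The sponsor should say which was intended, and disclose any hazard-scale or non-adherence assumption behind the 175.
- Align 9.1 and Aim 1 with the composite in 2.3.1: give its assumed control rate and the difference detectable with 175 per arm at 80% power. For assumed control rates from 45.6% to 70%, that difference is 14.4-14.9 points, or 15.0-15.5 with continuity correction.

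Restating these figures is a change of wording only, with no effect on enrolment or analysis. The enrolment target would need a fresh look only if the sponsor declares an effect that 175 per arm cannot detect, such as an odds ratio of 0.6 (254 per arm), or if the detectable difference on the composite proves unrealistic once its assumptions are stated.

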9.2 Data Analyses Plans

To account for the multiple measurements per patient, we will employ repeated measure regression techniques. Measures of relative risk will include 95% confidence intervals. Descriptive statistics will be presented as mean with standard deviation, median with interquartile range, or proportion with 95% confidence interval based on data type and distribution. Comparisons between groups will be performed using a Chi-square or Fisher's exact test for categorical variables and parametric or non-parametric tests for continuous variables, as appropriate. Bivariable analysis will be used to determine variables (risk factors) that are independently associated with PPHTN. Intention-to-treat analyses will be conducted such that all patients with available follow-up measures will be included in the analysis. Blood-pressure measurements after randomization will be compared between groups with the use of a mixed-effects logistic-regression model, which will account for participants having different numbers of observations over a varying time span. Statistical analyses were conducted in SAS, version 9.4 (SAS Institute, Cary, NC). Two-tailed P values of <0.05 will be considered statistically significant.

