Furosemide for Accelerated Recovery of Blood Pressure Postpartum: a randomized controlled trial (FoR BP trial)

A randomized, double-blind, placebo-controlled single center investigation of furosemide's effect on postpartum blood pressure control in pregnancies affected by hypertensive disorders of pregnancy

Protocol date: July 19, 2018

NCT#03556761

Furosemide for Accelerated Recovery of Blood Pressure Postpartum: a randomized controlled trial (FoR BP trial)

A randomized, double-blind, placebo-controlled single center investigation of furosemide's effect on postpartum blood pressure control in pregnancies affected by hypertensive disorders of pregnancy

Principal Investigator: [name], MSCE

Assistant Professor

Division of Maternal Fetal Medicine

Department of Obstetrics and Gynecology

[name]

[name]

Sub-Investigator(s): [name] [name]

Clinical Fellow

Division of Maternal Fetal Medicine

Department of Obstetrics and Gynecology,

Study Drug/Study Device: Furosemide (Lasix)

LIST OF ABBREVIATIONS

AE Adverse Event

CTCAE Common Terminology Criteria for Adverse Events

DSMB Data and Safety Monitoring Board

gHTN Gestational hypertension H&P History & Physical Exam

HRPP Human Research Protections Program
HDP Hypertensive disorders of pregnancy

[figure not shown]
HTN Hypertension IV (or iv) Intravenously

PI Principal Investigator
PO per os/by mouth/orally
PPHTN Postpartum hypertension

PR Partial Response

SAE Serious Adverse Event

STUDY SCHEMA

STUDY SUMMARY

Title	Furosemide for Accelerated Recovery of Blood Pressure Postpartum: a randomized controlled trial			
Short Title	FoR BP trial			
Methodology	Double blind, randomized, placebo control design			
Study Duration	20 months			
Study Center(s)	Single-center			
Objectives	To investigate the impact of a short course of furosemide on postpartublood pressure recovery in women with hypertensive disorders of pregnancy (HDP).			
Number of Subjects	385			
Diagnosis and Main Inclusion Criteria	Clinical disease state under study: hypertensive disorder of pregnancy, postpartum with delivery >20 weeks EGA, diagnosis of HDP antepartum, intrapartum and up to within 1 day of delivery			
Study Product(s), Dose, Route, Regimen	Furosemide (Lasix), 20mg, PO, daily			
Duration of administration	5 days			
Reference therapy	Placebo			
Statistical Methodology	Intention to treat analysis, chi-square tests for categorical variables, two-sample t-test for continuous variables			

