2.3.2 Secondary endpoints

- 2.3.2.1 Number of readmission/ ER visit that is hypertension related
- **2.3.2.2** Frequency of severe hypertension (SBP>160mmHg or DBP>110mmHg)
- **2.3.2.3** Number of days required until blood pressure resolution (<140/90 for 2 days)
- 2.3.2.4 Postpartum length of stay
- 2.3.2.5 Complications during hospitalization related to hypertensive disorders of pregnancy (acute pulmonary edema, acute kidney injury, disseminated intravascular coagulation, stroke or myocardial infarction, eclampsia, ICU stay, maternal death)
- **2.3.2.6** Adverse effects secondary to furosemide

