4.5 Duration of Follow Up

Patients will be followed for 10 days after discharge. All patients that consent to the study will be expected to enroll at an established program at the Hospital of the University of Pennsylvania to monitor blood pressures postpartum through daily texting. Patients will be expected to measure their blood pressures at least once daily and text them to a physician through the program. The program, Heart Safe Motherhood, has been utilized successfully over the past year to follow-up women after discharge and be more readily available to monitor blood pressures and give advice. Patients removed from treatment for unacceptable adverse events will be followed until resolution or stabilization of the adverse event.

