5.4 Follow-up Procedures

Prior to patient discharge, a research coordinator will ensure that the patient has the correct amount of pills left and will review instructions about taking the pill daily for however many remaining doses there are. If patients are breastfeeding exclusively, the

research coordinators will ask the patients upon discharge if they encountered any difficulties with breastfeeding while in the hospital. Patients will be followed for 10 days after discharge through Heart Safe Motherhood, a texting program offered at the Hospital of University of Pennsylvania in which women with HDP take their own blood pressures at home, and report those blood pressures through a texting service. A physician who is part of the study, will review the blood pressures daily and notify patients if more blood pressures, medications, or medical attention are needed. All patients in the study will be asked to text through the program their daily blood pressure and an affirmation that they are taking the remaining daily doses of furosemide/placebo at home. All patients, regardless of whether they are in the study or not, are expected to have a 6 week postpartum appointment. Participants will be asked to bring any remaining pills with them to that appointment at which time a research coordinator will collect the remaining pills, and record how many doses were missed. Any pills brought back by the patient will be given back to IDS to dispose of them. The research coordinator will also ask questions regarding any breastfeeding issues at this time. Furthermore, the charts of breastfed neonates will be followed to determine NICU admission or readmission during the first 6 weeks postpartum.

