5.5 Study schedule

Procedure	At Enrollment	Within 1 day of delivery	Postpartum, in house	Postpartum, at home	Up to 10 days after discharge	Postpartum 6 weeks
Inclusion/exclusion and demographics	Х	Х				
Randomization	Х	X				
Start intervention/ placebo		Х				
Intervention/placebo			X	X		
Blood pressure collection	Х		X	X	Х	X
Maternal outcomes						X

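### Days to blood-pressure resolution (Aim 2, endpoint 2.3.2.3) is right-censored 10 days after discharge, but the plan gives it only a t-test or an unspecified test for continuous data

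*Combined protocol and SAP*

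**What the plan says.** Aim 2 (section 2.2) is "To compare the time (days) required to achieve a resolution of elevated blood pressure". The matching secondary endpoint, 2.3.2.3, is "Number of days required until blood pressure resolution (<140/90 for 2 days". The next endpoint, 2.3.2.4, is "Postpartum length of stay".

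Section 4.5 sets the observation window: "Patients will be followed for 10 days after discharge". Section 5.4 sets the data stream inside it: "All patients in the study will be asked to text through the program their daily blood pressure". In the study schedule (section 5.5), the row "Blood pressure collection" is also ticked at 6 weeks.

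For analysis, the Statistical Methodology line of the Study Summary gives a "two-sample t-test for continuous variables". Section 9.2 gives "parametric or non-parametric tests for continuous variables, as appropriate". Section 9.2 also plans repeated-measures regression for multiple measurements per patient and a mixed-effects logistic model for blood-pressure measurements, and it includes every patient who has follow-up measures. The plan does not mention Kaplan-Meier, log-rank, Cox or any other time-to-event method, censoring, a time origin for this endpoint, or a value for a woman who has not resolved.

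**The concern.** The endpoint is a time to an event, seen through a window that closes. A woman who has not had her two days below 140/90 when daily texting ends has no known day of resolution, only a lower bound. The single 6-week reading cannot show two days or date them. A t-test needs a number for her and a rank test needs a rank, and the plan supplies neither. The mixed logistic model estimates the odds of an elevated reading, which is a different quantity from days to resolution.

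The window also closes on a different day for each woman, because it runs from discharge. Length of stay is itself an outcome, so a method that enters the cut-off day as if it were the resolution day mixes two endpoints.

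At stake is the interpretation of one of the trial's two aims: the size of the difference in days, some power, and an analysis choice left open until the data are seen.

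**Working it through.** **1. The plan's own figure.** The only computed figure is the section 9.1 sample size, which is for the day-7 binary outcome. Losses: 2 × 175 × 1.10 = 385, so 175 reads as per arm. A 40% relative reduction from 45.6% is 0.456 × 0.6 = 27.36%. A standard two-proportion calculation (80% power, two-sided 5%) then needs 109 per arm, so 175 is not reproduced; 175 per arm gives 80% power for about 31%. That mismatch is a separate matter. It is used here only to justify running both 27.36% and 31% as furosemide scenarios. No figure exists for days to resolution.

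**2. Assumptions (not in the documents).**
- 173 per arm: 385 × 0.9 / 2 = 173.
- The share elevated at day 7 stands in for the share unresolved at day 7.
- The share unresolved at day t is S(t) = s^((t/7)^k), where s is the day-7 share and k is 1 (exponential), 1.5 or 2 (lightest tail).
- Discharge is on day 2, 3 or 4 with weights 35%, 50% and 15%, so daily data end on day 12, 13 or 14.

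**3. Unresolved at the cut-off, by hand for k = 1.**
- Placebo: S(12) = 0.456^(12/7) = 0.260, S(13) = 0.233, S(14) = 0.208. Weighted: 0.35 × 0.260 + 0.50 × 0.233 + 0.15 × 0.208 = 0.239.
- Furosemide at 27.36%: 0.35 × 0.108 + 0.50 × 0.090 + 0.15 × 0.075 = 0.094.

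**4. Simulation, 1,500 trials per row.** Power in %. The last column is the mean difference in days, first capped at each woman's own cut-off, then restricted to day 10.

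| k; furosemide at day 7 | Unresolved %, placebo / furosemide | Log-rank | Capped t-test | Ranked last | Capped / day 10 |
|---|---|---|---|---|---|
| 1; 27.36% | 23.7 / 9.4 | 99.0 | 97.9 | 96.8 | 1.79 / 1.35 |
| 1; 31% | 23.8 / 11.8 | 92.8 | 88.3 | 87.8 | 1.45 / 1.07 |
| 1.5; 27.36% | 14.6 / 4.2 | 99.7 | 99.3 | 98.4 | 1.60 / 1.22 |
| 1.5; 31% | 14.4 / 5.6 | 93.7 | 90.1 | 87.9 | 1.28 / 0.96 |
| 2; 27.36% | 7.4 / 1.4 | 99.7 | 99.3 | 98.5 | 1.40 / 1.10 |
| 2; 31% | 7.5 / 2.2 | 95.3 | 91.7 | 89.7 | 1.12 / 0.87 |

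The largest loss against log-rank is 93.7 − 87.9 = 5.8 points. A separate exponential simulation (175 per arm, cut-off day 12 or 13) with a smaller effect, hazard ratio 1.3, gave log-rank 62.1%, capped t-test 54.9% and capped rank test 53.3%. Those are losses of 7.2 and 8.8 points.

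**5. Size of the difference, k = 1, cut-off day 12.** With daily rates 0.1122 (placebo) and 0.1852 (furosemide):
- Uncensored means: 8.91 − 5.40 = 3.51 days.
- Capped at day 12, mean = (1 − S(12))/rate: 6.59 − 4.82 = 1.78 days.

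A restricted mean is also shorter than 3.51, but it states its horizon and uses the same one in both arms.

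**6. No blood-pressure effect, stay one day shorter on furosemide.** Moving the cut-off from day 13 to day 12 lowers the capped mean by (0.2602 − 0.2326)/0.1122 = 0.25 day with no change in blood pressure. Simulated false positives (4,000 trials; k = 1, 1.5, 2): capped t-test 8.3, 8.4 and 6.7%; log-rank 4.9, 5.8 and 5.4%. A further 3,000 trials at k = 2 gave 5.4% for the capped t-test, so the drift there is small. Allowing for variation between simulations, about 7-11% is a fair range for the heavier tails.

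**The case against.** The strongest reply is that section 9.2 already allows a workable analysis. A rank test with unresolved women placed last fits its wording, uses every woman, and loses little power. With equal stays, each rule taken alone keeps about 5% false positives, and choosing between capping and ranking last after seeing the data gives only about 6%. This stands, and it limits the claim: the planned tests are not invalid in themselves. What remains is that the plan neither chooses such a rule nor describes one, while the Study Summary names the t-test.

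A reader might infer that unresolved women will be dropped. Under that rule power falls to 34-78% for k = 1 and 1.5 (74-93% for k = 2), and choosing the best of dropping, capping and ranking last gives 8-9% false positives. The documents do not support that reading. An unresolved woman who texts daily has follow-up measures, and section 9.2 includes all such women. Dropping is a worst case only.

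The stay scenario is also hypothetical. The trial is blinded, section 5.3 gives the same routine stays for both arms, and nothing suggests a full day's difference.

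The inputs are weakly anchored. A woman elevated on day 7 may already have had two normal days. Added amlodipine (section 4.3) is not modelled. Section 1.1 cites 28 to 57% normalised within 3 days; k = 1 implies 1 − 0.456^(3/7) = 29%, but k = 1.5 and 2 imply 20% and 13%. Those rows serve only as lighter-tail sensitivity cases.

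**Conclusion.** The point holds at moderate size. Aim 2's endpoint is right-censored at a cut-off that varies by woman, and neither stated test for continuous outcomes handles women still unresolved. Under the assumptions above, about 7-24% of placebo and 1-12% of furosemide women would be affected. With capping or ranking last, the power loss is at most about 6-9 points. A capped t-test understates the difference in days (1.8 against 3.5 in the exponential case) and could read a shorter stay as faster resolution.

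The gap itself rests on the text; only its size rests on the assumed distribution, discharge days and day-7 proxy. The endpoint is secondary, and the primary composite and sample size are untouched.

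A reader might go further and say that the resolution definition is faulty, because section 1.3 describes an early fall in pressure followed by a rise, or that sustained resolution is needed. That is not part of this point: neither definition performs better in every case examined, so no error is shown.

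**What to change.** In section 9.2:
- Analyse days to resolution as a time to event in all randomized women with follow-up, from a named origin (delivery or randomization).
- Keep the existing event, and state that the two days below 140/90 are consecutive.
- Censor women without the event at their last daily reading, and report the number censored by arm.
- Report Kaplan-Meier curves, a log-rank test stratified by the severe-features randomization factor (section 5.2), and a hazard ratio or a restricted mean time to a common day. Day 10 is one choice, since planned follow-up reaches it whatever the day of discharge.
- Bring the t-test line in the Study Summary into agreement.

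The cost is one paragraph and slightly more analysis work, using daily readings that are already collected. Censoring at the last reading assumes that stopping texting is unrelated to blood pressure, so the censoring counts by arm should be shown. The primary endpoint and sample size do not change.

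### Section 9.2 assigns bivariable analysis the task of finding independent associations with PPHTN, but it yields only unadjusted ones (minor; exploratory analysis only)

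*Combined protocol and SAP*

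**What the plan says.** The risk-factor analysis is one sentence in section 9.2: "Bivariable analysis will be used to determine variables (risk factors) that are independently associated with PPHTN". It names no candidate factors, covariates or selection rule.

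The other methods in section 9.2 are:

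- Unadjusted tests: "Comparisons between groups will be performed using a Chi-square or Fisher's exact test for categorical variables and parametric or non-parametric tests for continuous variables".
- A regression for repeated readings: "To account for the multiple measurements per patient, we will employ repeated measure regression techniques".
- A regression for the comparison of arms: "Blood-pressure measurements after randomization will be compared between groups with the use of a mixed-effects logistic-regression model".
- The significance threshold: "Two-tailed P values of <0.05 will be considered statistically significant".

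The Statistical Methodology row of the Study Summary lists "Intention to treat analysis, chi-square tests for categorical variables, two-sample t-test for continuous variables" and no multivariable model.

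Elsewhere, section 5.2 stratifies randomization by presence of severe features, and section 10.2 collects demographic, obstetrical, medical and delivery data. These are the likely source of candidate factors. The aims (sections 2.1 and 2.2) and endpoints (section 2.3) do not mention risk factors.

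**The concern.** The method and the conclusion drawn from it do not match. A bivariable test estimates a marginal association: how the outcome differs by one factor, with everything else left to vary. An independent association is conditional, meaning what remains once the other factors are held fixed. The two agree only in special circumstances, such as candidate factors that are uncorrelated with the other causes of the outcome.

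That is not a safe assumption here. Randomization balances treatment arm against baseline factors, but it does not balance baseline factors against one another. The protocol treats severity as important enough to stratify on, and obstetrical and delivery variables can plausibly correlate with it. A variable with no link to postpartum hypertension beyond that correlation could pass a bivariable test at 0.05 and then be described, following the plan to the letter, as an independent risk factor. What is at stake is the accuracy of that one secondary output.

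**Working it through.** **1. Do the documents supply an adjusted model elsewhere?** The plan gives no figure to reproduce on this point, so the first check is a reading of the analysis text.

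| Method named | Stated purpose | Adjusts one risk factor for another? |
|---|---|---|
| Chi-square, Fisher, parametric or non-parametric tests (9.2) | Group comparisons | No |
| Repeated-measures regression (9.2) | Several measurements per patient | Not stated; no covariates listed |
| Mixed-effects logistic regression (9.2) | Post-randomization blood pressure by arm | Not stated; no covariates listed |
| Chi-square, t-test (Study Summary) | General methodology | No |
| Bivariable analysis (9.2) | Independent risk factors | No, by definition |

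Neither regression is tied to risk factors, and no second, adjusted step follows the bivariable one.

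**2. How large could the effect be?** This is an illustration. Its inputs are:

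- N = 385 × 0.9 = 346.5, taken as 347 (section 9.1: 385 randomized, about 10% losses).
- Two-sided alpha 0.05 (section 9.2).
- Overall event rate about 36.5%. Section 9.1 reports that "45.6% of patients had persistently elevated blood pressures 7 days after delivery" and assumes a 40% reduction, so the treated rate is 0.456 × 0.6 = 27.4% and the mean is (45.6 + 27.4)/2 = 36.5%. Averaging the arms is an assumption.
- X1, a true risk factor with prevalence 50% and odds ratio 2 or 3 (assumed).
- X2, with prevalence 50%, correlation r = 0.3 or 0.5 with X1, and no effect of its own (assumed).

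The share of women with X1 is q = (1 + r)/2 when X2 is present and 1 − q when it is absent. With event rates p1 (X1 present) and p0 (X1 absent), the marginal rates by X2 are:

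- A = q·p1 + (1 − q)·p0 (X2 present)
- B = (1 − q)·p1 + q·p0 (X2 absent)

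The logistic intercepts used, −0.91 and −1.13, give p0 = 28.7%, p1 = 44.6% for odds ratio 2, and p0 = 24.4%, p1 = 49.2% for odds ratio 3.

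Worked case, odds ratio 2 and r = 0.3, so q = 0.65:

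- A = 0.65 × 0.446 + 0.35 × 0.287 = 39.0%
- B = 0.35 × 0.446 + 0.65 × 0.287 = 34.3%
- Bivariable odds ratio = (0.390/0.610)/(0.343/0.657) ≈ 1.23, although X2 does nothing.
- The pooled rate is 36.65%. With 173.5 women per X2 group, the standard error is √(2 × 0.3665 × 0.6335/173.5) = 0.0517.
- Expected z = (0.3903 − 0.3426)/0.0517 = 0.92, and the chance of p<0.05 is about 15%.

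All four settings, with simulated results from 1,500 trials each (chi-square for X2 alone; logistic model with X1 and X2 for the adjusted test):

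| True OR of X1 | r | A vs B | Bivariable OR of X2, by formula | p<0.05 bivariable, by formula | p<0.05 bivariable, simulated | p<0.05 adjusted, simulated |
|---|---|---|---|---|---|---|
| 2 | 0.3 | 39.0% vs 34.3% | 1.23 | 15% | 16% | 5% |
| 2 | 0.5 | 40.6% vs 32.7% | 1.41 | 34% | 32% | 6% |
| 3 | 0.3 | 40.5% vs 33.1% | 1.38 | 30% | 30% | 3% |
| 3 | 0.5 | 43.0% vs 30.6% | 1.71 | 67% | 65% | 6% |

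Formula and simulation agree closely. The simulated bivariable odds ratios run from 1.24 to 1.71, and the adjusted ones are about 1.0. The adjusted rejection rates sit near the nominal 5%.

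**The case against.** The strongest reply is about weight. Risk-factor identification is not one of the two aims and not among the primary or secondary endpoints; it appears in a single sentence with no factors named. An error there changes no efficacy or safety conclusion, no sample size and no data collection. This stands, and it sets the severity.

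The second reply is that the word claiming independence may have been used loosely, for screening variables one at a time. That is plausible, and if so deleting one word cures the sentence. As written, though, the bivariable step itself is what determines independence, so the text still needs changing.

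The third reply is that the illustration rests on assumed odds ratios, prevalences and correlations. That also stands: the range shows direction and possible size, and it is not a forecast for this trial.

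Two stronger readings are tempting. A reader might infer that confounded factors would certainly be reported as independent. The documents do not support that: they do not say which factors will be tested or how these correlate, and in three of the four settings above the factor with no effect escapes detection more often than not. A reader might also infer that the trial's main result is compromised. It is not, because the comparison of furosemide with placebo rests on randomization and does not use this analysis.

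**Conclusion.** The point holds, and it is minor. The sentence in section 9.2 gives a method that cannot support its stated conclusion, and nothing else in the documents supplies the missing adjustment. Factors correlated with severity or with another factor could be reported as independent. That part of the conclusion is a matter of definition and needs no assumed figure.

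The size does depend on assumptions. With about 347 women, a true-factor odds ratio of 2 to 3 and a correlation of 0.3 to 0.5, a factor with no effect of its own is flagged in about 16% to 65% of trials by bivariable testing, against 3% to 6% after adjustment. Weaker correlation or a weaker true factor would bring the first figure down towards 5%. The consequence is confined to the exploratory risk-factor output.

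**What to change.** Choose one of two amendments to section 9.2.

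- **If independent associations are wanted:** replace the sentence with a multivariable model, for example modified Poisson or logistic regression, for the composite in section 2.3.1. Include treatment arm, the severity stratum used in randomization, and a short list of baseline factors fixed before unblinding. State that bivariable results are descriptive only. Naming the composite also settles which outcome PPHTN denotes, since section 9.2 does not say whether it means the composite or elevated pressure alone. Modified Poisson would sit naturally with the relative risks that section 9.2 already plans to report.
- **If they are not wanted:** delete the word claiming independence and label the results as unadjusted associations.

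The first option costs one rewritten sentence, one extra model and agreement on the factor list. The second costs one edit. Neither needs data beyond what section 10.2 already collects.
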